10.5 Safety Meetings

Monthly teleconferences will be scheduled to include the PI/Sponsor, site Principal Investigators, Coordinating Center representatives, Site representatives and Celgene representatives (as appropriate). During these meetings, the Investigators shall provide the Coordinating Center with study progress updates. The Investigators will provide a summary of key points from the weekly meetings with a focus on safety of the protocol participants, enrollment status, and progress of data for objectives. In addition, Celgene will provide safety and applicable program updates to the Sponsor.

11 Biostatistical Analysis

11.1 Study Design/Endpoints

This trial is a phase II trial with the primary endpoint to demonstrate an increase in progression free survival in the CC-486 arm (Arm A) as compared to the observational arm (Arm B). Secondary endpoints include determining the response rate to chemotherapy, overall survival, and hypomethylation seen in the CC-486 arm as compared to the observational arm.

11.2 Study Populations

11.2.1 Efficacy Evaluable Population

The primary comparisons will include all randomized patients according to the assigned treatment groups (i.e. 'as randomized'). Secondary sensitivity analyses will examine the subset of patients receiving at least 1 dose of study drug as well as the subset of patients receiving at least 1 dose of chemotherapy. Comparisons of individuals based upon treatment received will also be examined as a sensitivity analysis.

11.2.2 Methylation Analysis Population

The methylation analysis population will consist of all subjects with any evaluable methylation results including plasma and/or tumor biopsies.

11.3 Statistical Methodology

11.3.1 Efficacy Analyses

Progression free survival is defined as the time from randomization until visible recurrence on any imaging modality, a confirmed biopsy, or death. Individuals lost to follow-up prior to having an event will be censored at the time of the last scan or biopsy. In the case of an equivocal scan reading, the patient will be re-imaged on schedule, if clinically appropriate, and if subsequent reimaging confirms recurrence, the event will be considered to have occurred at the first time point when a related abnormality was noted. Overall survival is defined as the time from enrollment until death. Individuals lost to follow-up prior to death will be censored at the time of last physician contact.

Time to event outcomes, including the primary endpoint progression free survival and overall survival, will be summarized using Kaplan-Meier estimates of the survival function. From these estimates, median time to event and one-year survival proportions with 95% confidence intervals will be extracted. Cox proportional hazards models will be used to compare the two treatment arms and to evaluate and adjust for potential prognostic factors (e.g. nodal status, microscopic margins, increase in CA19-9, therapy). The number and type of responses to chemotherapy will be tabulated for each group. Logistic regression will be used to compare the response rate between the groups and to identify risk factors associated with response. Results will be considered statistically significant for p-values < 0.05.

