2.2 Schedule during Follow Up – All Subjects*

Assessments are to be completed within 3 months of safety assessment/progression/previous follow-up

Schedule variations for CA19-9 and Imaging assessments permitted

Procedure *	Follow Up (Until 2 nd disease progression)	Survival Follow-Up ^{**} (≤ 3mo of previous follow up)
Information on new cancer therapies (records to be obtained)	Х	
Subjective response to therapies (records to be obtained)	Х	
CA 19-9 (records to be obtained)	Х	
Imaging completed (records to be obtained)	Х	
Study team contact***	Х	Х

- * For Arm B patients, follow up will be completed within 3 months of cycle 10 or within 3 months of disease progression. For Arm A patients, follow up will be completed within 3 months of safety assessment. If safety assessment was not completed, follow up will begin within 3 months of progression/discontinuation of drug. Follow Up assessments are ideally to be completed on a 3 month schedule, in which subsequent follow ups will be completed within 3 months of the previous follow-up. However, CA.19 and Imaging may be completed per the patient oncologist's discretion. An attempt to contact patients and obtain information on new cancer therapies and subjective responses to such therapies will occur within 3 months of the previous follow up.
- ** Survival Follow-Up will begin once the patient is deemed to have progressive disease for the second time. If the patient has not progressed and was put on Follow Up for reasons other than visible disease progression, patient must still have two instances of visible disease progression until being on the Survival Follow Up schedule. Patients will remain on the selected Follow-Up schedule for a combined total of up to 4 years, death or the subject withdraws consent (whichever occurs first).
- *** Study team will attempt to contact the patient in order to obtain information regarding his/her survival status, and any other comments/information per PI's request. While it is preferred the study team contacts the patient for follow-up, this information may also be obtained through medical records and obituaries.

3 Background and Rationale

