5.3.2.2 Arm A for first 12 cycles

Arm A patients will be evaluated on Day 1 of every cycle with a physical examination, ECOG performance status, vital signs, weight, CBC with differential, research blood and serum chemistry and hepatic panel. Arm A patients will also complete an assessment of adverse events and reporting of current medications/procedures on Day 1 of every cycle.

Arm A patients will complete a CA 19-9, quality of life assessment and CT scan on Day 1 of every third cycle beginning at Cycle 4.

Arm A subjects will be evaluated for adverse events on Day 1 of each cycle with the NCI CTCAE v4.0 (http://ctep.info.nih.gov) used as a guide for the grading of severity. For Arm A patients, doses will be reduced for hematologic and other non-hematologic toxicities that can be attributed to the study drug. Dose adjustments are to be made according to the system showing the greatest degree of toxicity. When a dose reduction is required for Day 1 of any cycle, no dose re-escalation will be permitted for the duration of study treatment.

NOTE: Arm B patients will not be evaluated for adverse events as they do not receive the study agent.

Criteria to Initiate Treatment

In Arm A, a new course of treatment may begin on the scheduled Day 1 of a new cycle if:

- Absolute neutrophil count $\geq 1500/\text{mm}^3$
- Platelet count $\geq 100,000/\text{mm}^3$
- Serum creatinine levels < 2 mg/dL
- Serum bilirubin levels $\leq 1.5 \text{ mg/dL}$.
- AST (SGOT) and ALT (SGPT) \leq 2.5 x the institutional upper limit (ULN) of the normal range
- Any other drug-related adverse events that may have occurred must have resolved to < Grade 2 severity except grade 2 anorexia and any correctable metabolic abnormality.
- No evidence of visible disease recurrence on imaging (if indicated per Study Schedule, Section 2, to be done prior to cycles 4, 7, and 10)

If these conditions are not met on Day 1 of a new cycle, the subject will be evaluated weekly and a new cycle of treatment will not be initiated until the toxicity has resolved as described above utilizing the dose modifications as depicted below. If the study drug has to be held for > 28 days, study treatment will be discontinued.

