5.3.2.3 Arm B for the first 12 cycles

Arm B patients will ideally be evaluated (or at the very least contacted by the study team) on Day 1 of every third cycle beginning with Cycle 4.

Patients are permitted to see their local oncologist, and CA19-9 and lesion assessments may be completed outside of the recommended 3 month window (Cycles 4, 7, and 10) at their oncologist's discretion.

Arm B patients will follow a similar schedule as patients in Follow-up, except for a Quality of Life assessment that will be performed.

Correlative blood draw is optional for Arm B patients. If Arm B patients wish, they may have research bloods drawn for correlative studies.

Arm B patients who opt to have research blood collected will have it collected on Day 1 of every third cycle (cycle 4, 7 and 10).

Below is the list of information that must be obtained from Arm B patients.

- Any further therapy received (records to be obtained)
- Subjective response on therapy (records to be obtained)
- Any CA 19-9 drawn (records to be obtained)
- Any imaging (images to be obtained)

Arm B patients will complete a CA 19-9, quality of life assessment and CT scan (or alternate imaging, if clinically indicated) quarterly (ideally).

Arm B patients who are not evaluated in person may have the Quality of Life assessment completed over the [contact] Dose Modification

Table 5.3.1: Arm A: Dose Modification Recommendations for CC-486 Phase
--

Toxicity	Grade	CC-486
Febrile Neutropenia	Grade 3 or 4	Hold until resolved and neutrophils \geq 1500/mm ³
		Restart study drug at 200 mg (two tablets, 33% dose reduction).
		If the same Grade 3 or 4 event recurs (i.e., third occurrence) despite CC-486 dose reduction to 200 mg, as described above, permanently discontinue study
Leukopenia and/or Neutropenia	Grade 2-3Hold dose until recovery to Grade ≤ 1 or baseline.Resume study drug at prior dose	
	Grade 4	Hold until resolved to \leq Grade 1
		Restart study drug at 200 mg (two tablets, 33% dose reduction).
		If the same Grade 4 event recurs (i.e., third occurrence) despite CC-486 dose reduction to 200 mg, as described above, permanently discontinue study drug.
Thrombocytopenia	Grade 1* or 2	Hold treatment until resolution to normal values.
	Grade 3 or 4	Hold until resolved and platelet count ≥100,000/mm ³ Restart study drug at 200 mg (two tablets, 33% dose reduction)
Diarrhea (unresponsive to maximum medical	Grade 1 or 2	Consider administering symptomatic remedies and/or start prophylaxis.

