5.5 Follow-up Phase Both Arms

No disease recurrence:

Less than 10% of patients who have undergone surgery will not develop tumor recurrence after adjuvant therapy.

Therefore, if patients have not recurred after one year of therapy with CC- 486 (Arm A) the drug will be discontinued.

Patients in Arm A will undergo a safety assessment 28 days (\pm 2 days) post the last dose of protocol therapy for resolution of toxicity.

Because Arm B patients do not receive study drug, a safety assessment will not be performed.

All patients (Arm A and B) will be then be contacted (ideally) every 3 months on to obtain the following information about recurrence, survival and anti-cancer treatment (2.2 Study Calendar):

- Any further therapy received (records to be obtained)
- Subjective response on therapy (records to be obtained)
- Any CA 19-9 drawn (records to be obtained)
- Any imaging (images to be obtained)

Disease recurrence

At the time of recurrence, Arm A and Arm B subjects will undergo biopsy of the recurrent lesion per the method determined best per the investigator.

Post recurrence images will be also obtained (pre-recurrence images are optional)

Thereafter, attempts to contact patients every 3 months in order to obtain lesion assessments/post recurrence images, CA19-9 and anticancer treatment and survival information as detailed in section 5.4.2. If study team is unable to make contact with patients, information may be obtained through medical and public records. This information will continue to be collected for patients until patients hit second disease progression.

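### The OS definition (enrollment start, censoring at last physician contact) does not match the plan's own vital-status follow-up or the PFS start; OS can be understated, by little at the planned 10% loss

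*Combined protocol and SAP*

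**What the plan says.** Section 11.3.1 gives the two time-to-event endpoints different origins. For the primary endpoint: "Progression free survival is defined as the time from randomization until visible recurrence on any imaging modality, a confirmed biopsy, or death". For OS: "Overall survival is defined as the time from enrollment until death". The OS censoring rule is: "Individuals lost to follow-up prior to death will be censored at the time of last physician contact". No rule is given for patients who are alive and still followed at data cut-off, and neither loss to follow-up nor physician contact is defined.

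Vital status is collected by other routes. Section 2.2: "Study team will attempt to contact the patient in order to obtain information regarding his/her survival status", and "this information may also be obtained through medical records and obituaries". Section 5.5: "If study team is unable to make contact with patients, information may be obtained through medical and public records". In the section 2.2 calendar, study-team contact is the only item marked for Survival Follow-Up. The earlier Follow Up column adds only records to be obtained. Follow-up lasts up to 4 years.

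Contact differs by arm in the initial phase. Section 5.3.2.2: "Arm A patients will be evaluated on Day 1 of every cycle with a physical examination". In Arm B, section 5.3.2.3 asks that patients ideally be evaluated every third cycle, "or at the very least contacted by the study team", and they may see a local oncologist. Section 5.1 puts both arms on one follow-up schedule after first progression.

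**The concern.** The censoring date is tied to a contact that the follow-up calendar does not schedule, and the contact that it does schedule is not used. Deaths can enter from an obituary long after the last physician visit. A survivor with the same contact history may be cut off at that visit. Removing event-free time only from people who have not died makes censoring depend on outcome and pushes the Kaplan-Meier curve down. If physician contact is lost more often, or earlier, in one arm, the hazard ratio (HR) moves as well.

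The wording also leaves room for two analysts to differ. One could censor a patient confirmed alive by telephone at the date of the call; the other could go back to the last clinic visit. OS is a named secondary endpoint and is compared by Cox model, so the result should not depend on that choice.

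**Working it through.** **The plan's own figures.** The documents give no power, event count or expected value for OS. The 10% loss comes from the PFS sample size in section 11.3.4, which reproduces. Take 54 evaluable patients (60 less 10%), medians of 6 and 9.84 months, 24 months' accrual and 12 months' minimum follow-up. The event probabilities are 0.915 and 0.793, so events = 27 × (0.915 + 0.793) = 46.1. Power = Φ(½ × √46.1 × ln 1.64 − 0.842) = Φ(0.838) = 79.9%, against the stated 80%. Nothing below changes this.

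**Size: inputs.**
- Follow-up at analysis uniform over 12 to 36 months (from the accrual and minimum follow-up in section 11.3.4).
- Exponential OS with median 18 months. This is an assumption; section 3.1 says only that median survival is under 2 years.
- All deaths counted. A share f of survivors is censored early by a mean gap g (f and g are assumptions).
- No true difference between arms.

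**Size: arithmetic.** The hazard is ln 2 / 18 = 0.0385 per month. The share alive at analysis is (e^(−12×0.0385) − e^(−36×0.0385)) / (24 × 0.0385) = (0.630 − 0.250) / 0.924 = 0.411. Person-time per patient is (1 − 0.411) / 0.0385 = 15.29 months. The rule removes 0.411 × f × g months from this and leaves the deaths unchanged, so the event-rate ratio A/B is

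(15.29 − 0.411 × f_B × g_B) / (15.29 − 0.411 × f_A × g_A).

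| Share of survivors affected, A / B | Mean gap in months, A / B | Event-rate ratio A/B |
|---|---|---|
| 10% / 10% | 1 / 3 | 15.17 / 15.25 = 0.99 |
| 10% / 10% | 1 / 6 | 15.04 / 15.25 = 0.99 |
| 10% / 30% | 1 / 6 | 14.55 / 15.25 = 0.95 |
| 10% / 50% | 1 / 6 | 14.06 / 15.25 = 0.92 |
| all / all | 1 / 1.5 | 14.67 / 14.88 = 0.99 |
| all / all | 1 / 6 | 12.82 / 14.88 = 0.86 |

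A simulation with 200,000 patients per arm agrees. The Cox HR is 0.985 for 10% in each arm with gaps of 1 and 6 months, and 0.995 with gaps of 1 and 3. With all survivors affected and gaps of 1 and 6 it is 0.84.

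**Effect on the median (same simulation, true value 18).** With 10% of survivors affected, mean gaps of 3, 6 and 12 months give 17.9, 17.8 and 17.6 months, a loss of 0.1 to 0.4. With all survivors affected, they give 17.0, 15.9 and 13.8.

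**What the bias depends on.** A second simulation assumed true medians of 12 and 20 months and contact gaps of up to 1 month (A) and 3 months (B), and varied how many deaths after loss of physician contact are counted.
- None counted: medians stay at about 12 and 20 and the HR at about 1.00. There is no bias when loss is unrelated to prognosis.
- All counted, 10% lost per arm: medians 11.8 to 11.9 and 19.3 to 19.4, HR 1.00. The largest loss is 0.7 months on 20.
- All counted, 10% (A) versus 30% (B) lost: HR 0.93 to 0.95. At 10% versus 50%: 0.85 to 0.90.
- Half counted: HR 0.96 to 0.97 and 0.91 to 0.94 for the same two contrasts.

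**Time origin.** OS from enrollment equals OS from randomization plus any interval d ≥ 0 between the two. The documents state no such interval. A positive d lengthens OS, and because it precedes allocation it is expected to be equal in the two arms.

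**The case against.** The strongest reply is that the rule is narrow. It covers patients lost to follow-up. Study-team contact is the planned follow-up, so a patient reached by telephone is, on the natural reading, not lost. On that reading no one known to be alive under follow-up is censored back; the plan merely omits the rule for patients alive at cut-off. This limits the size but does not remove the mismatch. A patient who is truly lost may have a study-team call later than the last physician visit, and the rule discards that time. The plan also leaves open whether a patient out of physician contact counts as lost.

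A reader might infer that the arms will be biased apart, with an HR near 0.84 in favour of CC-486, because Arm A is seen every 28 days. The documents do not support this. That figure needs the rule to apply to all survivors, whereas the plan allows for 10% loss. It also needs a mean Arm B gap of 6 months, which has no source: Arm B is recommended imaging and CA 19-9 every three months, and a local oncologist is a physician. With mean gaps of 1 and 1.5 months the ratio is 0.99 even if all survivors are affected. The 28-day visits last at most 12 cycles (336 days, about 11 months) and end at recurrence, for which the plan assumes a 6-month control median. After that, both arms share one schedule. No section suggests unequal loss such as 10% versus 30%.

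A reader might also infer that the enrollment origin contributes to understatement. It works in the other direction.

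**Conclusion.** The OS definition should be corrected, but on the plan's own loss figure the expected effect is small. The censoring date does not match the vital-status sources, and the origin matches neither PFS nor the as-randomized population of section 11.2.1. OS can be understated; that it will be is not established. Understatement requires deaths found in records to count while survivors are censored at an earlier physician visit.

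With 10% affected equally in both arms, the loss is about 0.1 to 0.4 months on an assumed 18-month median, and the HR under no effect is about 0.99 to 1.00. A material effect requires either applying the rule to most survivors or unequal loss of physician contact (HR about 0.95 at 10% versus 30%). Both are assumptions. The sizes also rest on exponential survival and on the assumed medians and gaps. PFS, its power and the futility rule are unaffected.

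**What to change.** Reword the OS definition in section 11.3.1:
- OS runs from randomization to death from any cause, and deaths count whatever the source.
- Every patient not known to have died, whether lost or alive at data cut-off, is censored at the date last known alive from any source (study-team contact, medical record, imaging or laboratory date).
- The rule and the search for vital status are the same in both arms.

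One condition matters. If deaths are picked up passively from obituaries but survivors are not looked for, part of the same bias remains. Vital status should therefore be sought for every patient at one common cut-off. In the second simulation, with vital status known for all, the medians return to the assumed 12 and 20 months and the HR to 1.00.

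The cost is a change of wording, a field for the date last known alive and its source, and the effort of the common check. The contacts and records are already part of the follow-up schedule. Sample size and the primary analysis do not change.

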11.3.2 Methylation Analyses

The correlative secondary studies will not affect sample size and are exploratory in nature only and are meant for hypothesis generation for further studies. Summary statistics (e.g. means, standard errors) and plots will be used to describe the pharmacodynamic endpoints at each time point (resection and relapse) as well as the change over time. T-tests will be used to assess the differences in the change in pharmacodynamic outcomes between those with and without CC486 exposure. These changes may also be quantified as a binary variable (response vs. no response) in which case the comparisons will be made using Fisher's exact test. Modeling approaches, which allow for the assessment of multiple variables, will also be considered for both the continuous outcomes (linear regression) and binary outcomes (logistic regression). A generalized estimating equation approach will also be considered to alleviate the impact of missing data on the inference.

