8.1 Plasma/Serum Samples

Blood for correlative studies will be drawn from all subjects in the study at screening and on Cycle 1 Day 1 prior to starting treatment. If screening assessments were done within 7 days of initiating Cycle 1 Day 1, these do not need to be repeated. Arm B patients have optional research blood draws on Day 1 Cycle 1 and on Day 1 of every third cycle (Cycle 4, 7, 10, etc.) thereafter. Blood for correlative studies will also be drawn from all patients at disease progression during the initial CC-486/observation phase. The blood samples will be used to assess the methylation status of free tumor DNA circulating in the blood. Both global and candidate gene methylation patterns

will be evaluated in plasma samples. Some of the potential candidate genes include: *TMS1*, *ARH1*, *hMLHI*.

Quantitative analysis using real-time Methylation-specific PCR (MSP) will be used to detect the presence of methylated alleles for specific genes. Genes found to be methylated in pretreatment samples will be monitored for changes during and after treatment using real-time MSP. DNA will first be extracted from plasma using standard phenol chloroform extraction. The DNA will then be analyzed for changes in DNA methylation at specific gene promoters that include *TMS1*, *ARH1*, *hMLHI*. PCR primers for these have been described and are in frequent use in the [name]/[name] lab. This strategy of real-time MSP has recently shown promising results in an ongoing trial in metastatic lung cancer with combination epigenetic therapy with subcutaneous 5-azacitidine and the HDAC inhibitor, entinostat.

We will also do methylation status analysis on samples using Methylation-on-Beads (MOB), a novel nano-enabled methylation based technology. This assay has shown great promise as a tool for surveillance of responses to epigenetic therapy in preliminary studies in solid tumors. The utility of the nano-enabled platform will also be explored in the ongoing correlative studies since this may provide a more sensitive assay for detection of response to epigenetic therapy than real time MSP.

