8.2 Tumor Biopsies

Tumor biopsies will be attempted on all subjects at the time of visible disease recurrence. We will also consent subjects to obtain paraffin-embedded blocks of their original resected pancreatic tumor. Methylation status will be assessed on these samples to correlate with the data received from the plasma analysis. All new biopsy specimens will be stored as fresh tissue at \leq -70°C for extraction of DNA and RNA.

All biopsy specimens will undergo tumor methylation analysis with MSP for select candidate genes (*TMS1*, *ARH1*, etc) as described above. Evaluation of expression of genes that become demethylated post-treatment will be performed using quantitative real-time PCR, whenever possible. Where sufficient tissue is obtained, samples will also be studied using an Infinium Methylation Assay that surveys genome-wide DNA methylation profiles (such as the Illumina HumanMethylation27 BeadChip or the newer Infinium HumanMethylation450 BeadChip). This technology examines approximately 27,500 CpGs in 14,500 regions, including 12,833 well-annotated genes described in the NCBI CCDS database, 144 methylation hotspots in cancer genes, 982 cancer related targets, and 110 microRNA promoters. Results are analyzed using BeadStudio software that allows for data analysis and integration of methylome data with mRNA or miRNA expression array studies. In regions of cancer hotspots, there are 7 CpGs studied on average per

gene. As little as 500ng of input DNA is required for the BeadChip, which allows for investigation of samples collected by laser capture microdissection. We will investigate if the Illumina Infinium chip can be used to define epigenetic signatures between responders and non-responders to oral epigenetic therapy.

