8.2.1.2 Archival Tissue

Patients will be consented in order for us to obtain paraffin-embedded blocks and slides of their original resected tumor. This will enable us to perform methylation analysis on the primary tumor and compare this to the tumors at the time of recurrence to determine if treatment with CC-486 led to any changes in methylation. The first slide should be stained for H&E (Hematoxylin and Eosin) for confirmation of the presence of tumor tissue; then, up to 20 serially cut slides should follow. Slides should be 10 microns in thickness and placed in tubes; alternatively, sections may be mounted on charged or silanted slides without coverslips. The H&E stained and all unstained slides will be submitted.

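### The methylation comparison uses unadjusted t-tests on change, although the resection value is collected and adjusting for it would be more precise

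*Combined protocol and SAP*

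**What the plan says.** Section 11.3.2 (Methylation Analyses) describes the outcomes at two time points and their change: "Summary statistics (e.g. means, standard errors) and plots will be used to describe the pharmacodynamic endpoints at each time point (resection and relapse"). The between-group test it commits to is: "T-tests will be used to assess the differences in the change in pharmacodynamic outcomes between those with and without CC486 exposure". If change is dichotomised, Fisher's exact test takes its place.

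Regression appears only as a possibility: "Modeling approaches, which allow for the assessment of multiple variables, will also be considered for both the continuous outcomes (linear regression") and logistic regression for binary ones. GEE is mentioned in the same conditional way, as a help with missing data. No covariate is named for any of these.

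The baseline value exists. Section 8.2.1.2 obtains the original resected tumour and says: "This will enable us to perform methylation analysis on the primary tumor and compare this to the tumors at the time of recurrence". The relapse value comes from section 8.2: "Tumor biopsies will be attempted on all subjects at the time of visible disease recurrence". For plasma, section 8.1 says: "Genes found to be methylated in pretreatment samples will be monitored for changes during and after treatment".

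Sections 1.1 and 4.2 list decreased methylation as secondary endpoint 3, and section 11.1 presents it as a comparison of the CC-486 arm with observation. Section 11.3.2 also sets the standing of the work: "The correlative secondary studies will not affect sample size and are exploratory in nature only".

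**The concern.** A t-test on change uses the resection value only by subtracting it, which fixes the slope of relapse on resection at 1. That is close to optimal only when the two measurements correlate strongly and share a scale. A regression estimates the slope from the data.

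The documents give some reason to doubt a slope near 1. The resection sample is paraffin-embedded primary tumour. The relapse sample is flash-frozen material from a core biopsy or fine-needle aspirate (sections 8.2 and 8.2.1.3), and may come from the primary site or a metastasis (section 2.1, note 13).

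Two things are at stake. The first is precision in a comparison with few pairs: at most 30 per arm, 27 after the plan's own 10% loss, and fewer once relapse and a successful biopsy are required. The second is that a chance difference in resection methylation between the groups passes into the difference in change. In the time-to-event analyses of section 11.3.1 the plan does provide for adjustment, with example prognostic factors. The methylation section has no counterpart.

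**Working it through.** **The plan's own figure.** No power, effect size, SD or correlation is stated for methylation. The only power figure is for PFS, and it reproduces. Exponential PFS with medians 6 and 9.84 months, 24 months' uniform accrual and 12 months' minimum follow-up gives event probabilities 0.915 and 0.793. With 27 evaluable per arm, events = 27 × (0.915 + 0.793) = 46.1. Power = Φ(ln 1.64 × √46.1 / 2 − 0.842) = 79.9%, against 80% stated. Nothing below changes this.

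**Inputs for methylation.** From the documents: two time points, an unadjusted t-test on change, and a collected resection value. Assumed: the same SD at both times (set to 1), correlation rho common to both groups, and n pairs per group.

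**Variances**, in units of (2/n) × SD²:
- change score: 2(1 − rho)
- baseline-adjusted: 1 − rho²
- ratio, adjusted to change: (1 − rho²) / [2(1 − rho)] = (1 + rho)/2
- estimating the slope multiplies the ratio by 1 + 1/(2n − 4): 1.038 at n = 15 and 1.0625 at n = 10

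| rho | change | adjusted | ratio | ratio, n = 15 | simulated, n = 15 | ratio, n = 10 |
|---|---|---|---|---|---|---|
| 0.3 | 1.40 | 0.91 | 0.65 | 0.675 | 0.67 | 0.691 |
| 0.5 | 1.00 | 0.75 | 0.75 | 0.779 | 0.79 | 0.797 |
| 0.7 | 0.60 | 0.51 | 0.85 | 0.883 | 0.89 | 0.903 |
| 0.9 | 0.20 | 0.19 | 0.95 | 0.987 | 0.99 | 1.009 |

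The simulated column uses 20,000 replicates per row. Below rho = 0.5, 2(1 − rho) exceeds 1, so raw change is noisier than the relapse value alone.

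**Chance imbalance.** Given a difference d in mean resection value between groups, the expected change-score difference shifts by (rho − 1) × d. In the simulation with 15 per group the shift per unit of d was −0.71, −0.50, −0.30 and −0.10 at rho 0.3, 0.5, 0.7 and 0.9. For the adjusted estimate it was about 0. Averaged over randomisations d is zero, so neither estimate is biased on average.

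**Illustration in power terms.** Assume a true difference of 0.8 SD, two-sided 0.05 and 15 pairs per group, with the normal approximation Φ(0.8 / √(variance × 2/15) − 1.96). Change-score power is 46%, 59% and 81% at rho 0.3, 0.5 and 0.7. Adjusted power is 63%, 72% and 87%, or about 62%, 70% and 85% once the 1.038 factor is included. The 0.8 SD is chosen only to show scale.

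**The case against.** The strongest reply is that this is exploratory, hypothesis-generating work with no power claim or decision rule, and that regression is already permitted. On that view a simple t-test first and a model second is a matter of taste. The low importance stands. The permission does not close the gap, because no covariate is named and nothing commits to the model, so the choice between t-test, Fisher's test and regression could be made after the data are seen.

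The sizes rest on assumptions about rho, the number of pairs and equal SDs, and paraffin and frozen samples may not have equal SDs. That also stands, and it is why a range is shown.

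A reader might infer more than the documents support:
- *That regression to the mean biases the comparison.* Following plasma genes because they were methylated before treatment makes values tend to fall in both groups. The between-group difference removes that shared fall on average, and only chance baseline imbalance remains.
- *That this is the trial's only pharmacodynamic evidence, or that the choice of test decides whether demethylation is seen.* Section 8 also plans plasma assays by two methods and expression of demethylated genes, and no decision hangs on a p-value here.
- *That adjustment would make the comparison a clean randomised one.* The groups are defined by exposure, among patients who relapse and yield evaluable tissue. Adjusting for the resection value does not remove that selection.

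**Conclusion.** The point holds as a minor, nearly cost-free improvement. The committed test leaves unused a baseline value that the trial already collects. Under equal SDs, adjustment cuts the variance by 35%, 25% and 15% at rho 0.3, 0.5 and 0.7, or by about 32%, 22% and 12% with 15 pairs per group. With about 10 pairs per group and rho near 0.9 the gain disappears (ratio 1.01), and little is lost by adjusting. Adjustment also takes out chance baseline imbalance, which the change score keeps in proportion 1 − rho.

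The finding concerns the precision of an unpowered exploratory analysis of secondary endpoint 3. It is not a finding of bias under intact randomisation, and it has no bearing on PFS, the futility rule, safety monitoring or the sample size of 60.

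**What to change.** In section 11.3.2, make the main between-group comparison for continuous methylation outcomes a linear model of the relapse value on treatment group, with the resection value as covariate. Modelling the change with the same covariate gives the same treatment estimate, so the outcome can stay as change if preferred. For any on-treatment plasma comparison, use the pre-treatment plasma value as the covariate. Keep the raw change and its t-test as descriptive or supportive results. State beside the result that it applies to patients who relapsed and had evaluable tissue.

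The cost is a sentence or two of SAP text and one degree of freedom. It needs no new samples, visits or patients.
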